Subjects should have a permanent address within the defined catchment area of the service. No age criteria will be used for inclusion but in practise 90% of patients will be over the age of 70. As this is a pragmatic trial exclusion criteria will be kept to a minimum. No more than a 3rd of patients will be from one single diagnostic category (e.g. not more than a third being stroke patients). We will record the presence of cognitive difficulties but will endeavour not to exclude patients because of such difficulties.

[figure not shown]
Recruitment

When referred for rehabilitation the patient will be assessed for suitability for rehabilitation and if defined as suitable, will be informed of the research with the help of a Patient Information Sheet (Appendix 4). If the patient agrees to research, then consent will be taken. Staff will make a professional judgement about whether assent of carer would be appropriate, (e.g. in cases of cognitive impairment), with the use of an Abbreviated Mental Test (assent taken if score below 7), or their instrument of choice. Where the AMT is not used to determine this, the researcher will perform the AMT to confirm the staffs decision.

Carers will be approached by a researcher with the permission of the patient following the baseline interview, and informed of the research with a Carer Information Sheet (appendix 6). If they agree to research consent will be taken and they will be interviewed at the 3 month follow up point.

A chart of anticipated recruitment is shown below which makes the following assumptions: Six sites. First site begins data collection in August 2004. Sites enter trial at 2 monthly intervals during 2004/5. Average 50 subjects per randomisation arm per calendar year available from each site. Assume start at smallest site. Figures adjusted for each site in proportion to annual day hospital rehabilitation throughput. This represents recruitment of about one third of potentially eligible patients from participating day hospitals and one seventh of potentially eligible patients from participating home rehabilitation services.

Projected recruitment

Randomisation, stratification and assessment

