Patients referred for rehabilitation will be routed through a central point. They will be assessed for their need for rehabilitation and the assessor will complete the Oxford Handicap Scale and Abbreviated Mental Test. The patient will be informed of the research using a Patient Information Sheet. If the patient consents to research they will be randomised to home based or day hospital rehabilitation following a baseline interview, using computer generated block randomisation within each centre, managed by an independent member of the research team and available during the normal opening times of conventional day hospital services. Feasibility of randomisation has been explored with professionals working in pilot and potential trial sites, and while there were some concerns there was a level of understanding about the necessity of randomisation. Time for piloting randomisation processes is built in to the running time in each site to accommodate local issues, and in the first sites to begin randomisation an initial period of piloting will test and resolve any problems in procedures. The scoping study will have identified variation between sites on a number of key variables (e.g. age distribution, range of clinical conditions, sources of referral), which will inform a final decision about stratification. Eligible patients will be stratified by source of referral (hospital inpatient or primary health care team) and the Oxford Handicap Scale using a cut point of 2/3. It is possible that patients will be referred for rehabilitation more than once in the course of the year that they are part of the research. Subjects re-referred to the trial will continue treatment in the arm of the trial to which they were first randomised and study follow-up will continue from the point of randomisation.

Informing GPs about the research

Prior to patient recruitment we will inform all GP surgeries local to the trial site about the research. As patients are recruited we will inform their GP's individually that they are a participant in the trial and that we will contact the GP prior to contacting the patient for follow-up, to check for death.

Outcome measures

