Outcomes will be assessed by interview but in addition (to assess potential bias due to ineffective blinding of interviewers) self-completed questionnaires will be completed by a randomly selected 50% of surviving subjects at 6 months and by the other 50% at 12 months. The primary outcome will be functional health status as measured using the Nottingham Extended ADL scale¹³. All outcomes will be measured at base line and at 3, 6 and 12 months after recruitment by interviewers who are unaware of the treatment allocation (see below). Carer interviews will take place within 1 month of patient interviews. Secondary outcome measures will include survival (death certifications) and changes in subject's perceived mental state (Hospital Anxiety and Depression Scale⁽¹⁴⁾), change in household or residential or nursing home circumstances (study records), informal caregiver's psychological health (General Health Questionnaire (GHQ)⁽¹⁵⁾) and patient's and informal caregiver's views of 'treatment' (semi-structured interviews). Therapy Outcome Measures (TOMS) will be used to measure outcomes in relation to rehabilitation aims.

Assessment of quality of life is implicit within the choice of outcome measures, (including EuroQOL). No generic and comprehensive quality of life measure is proposed since there is no evidence that a suitable measure exists for this particular patient group. Taken together the proposed outcome measures cover the traditional domains of quality of life included in generic measures. In the absence of reliable patient reported data, data collected from informal caregivers will be substituted where appropriate since previous studies have indicated that informants are a source of reliable data^(16 17 18). The applicants have used all the proposed outcome measures identified in recent studies and found them to be appropriate to the study.

Patient Interviews

Patients will be interviewed in their own homes, following prior arrangement by telephone or letter, by a researcher unaware of their treatment allocation. The interviews have been shown in the pilot to take between 30 minutes to an hour. Patients' welfare will be considered of paramount importance at all times. Proxy information will be used if the interviewer feels that the patient is not capable of answering questions accurately. This will be judged by a combination of AMT score and ability to answer pre-interview questions. The interview will

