consist of the instruments outlined in Table 2, and a short semi-structured interview to ascertain views of treatment.

Carer Interviews

It was found in the pilot study that many carers are present at the patient's interview, in which case consent will be taken then and their (see appendices 6 and 7 for Carer Information Sheet and Consent Form) and the interview carried out, in private with the carer where possible. If not, the researcher will ask permission to contact the carer, and then arrange with the carer to visit them at their home. The interview will consist of the instruments outlined in Table 5, and a short semi-structured interview to ascertain views of treatment. In the pilot this was estimated to take about 30 minutes.

Education of data collectors

The data collectors will be trained and monitored to ensure inter rater and intra rater reliability. There will be a 3-day training course at the start of the trial and refresher days will be organised during the trial. There was some discussion about the possible use of videos for this, but it was felt that the effort and expense of producing a video was likely to be more than organising a venue and travel for data collectors.

Data collectors/interviewers will be taught a standard procedure when asked to respond to or faced with a clinical problem during the interview (experience is that this is an uncommon occurrence). In addition, each data collector will be assigned an experienced mentor, who will be available for counselling over unfamiliar and/or potentially distressing experiences during interviews, and can be contacted in cases of concern and these will be logged.

Generalizability, cost and compliance

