32	Who do you live with at home? 
 With your husband/wife or a partner 1 With your children 2 With your parents 3 With a brother or sister 4 With some other person 5 No one - I live alone 6 
	338
33	Are you: 
 Married or living with a partner 1 Divorced or separated 2 Widowed 3 Single 4 
	339
34	Are you or your family members currently receiving any of the following allowances? 
 Jobseeker's allowance (Ex-Unemployment benefit) 01 Income support 02 Working tax credit (Ex-working families tax credit) 03 Statutory sick pay 04 Incapacity benefit (Ex-Invalidity benefit) 05 Severe disablement allowance 06 Health benefits 07 Attendance allowance 08 Carers allowance (Ex-Invalid care allowance) 09 Council tax benefit 10 Housing benefit 11 Disability living/allowance 12 State retirement pension 13 Disabled persons tax credit 14 Other (Please write in what) 15 Not receiving any 16 
	340 341 342 343 345 346 347 348 349 350
35	What is your date of birth?	351
36	(Record gender of patient). Male (1) Female (2)	352

Carer questionnaire

University of Sheffield Sheffield Institute for Studies on Ageing Rehabilitation of Older Patients: day hospital compared to rehabilitation at home – HTA Project No: 97/26/01	
Carer Interview Schedule	
Patient study number	1
Interviewer ([name]=1)	2
Interview done in home(1)/hospital(2)	3
Date	4
Baseline(0)/3 months (1)/6 months(2)/1 year(3)	5

1	So, when did you start to assist Mr/Mrs (Patients name)	6
2	What is your relationship to the person you are assisting? Are you: 
 His/her spouse/partner 1 His/her child 2 His/her grandchild 3 A friend 4 A paid carer 5 Other (please write in relationship) 6 
	7

3	
Which of the following best describes your current position about work? (Please ring one number only).
 
Full or part time 1 Retired 2 At home and not looking for paid employment 3 (eg looking after your home, family or other dependants) Unable to work due to illness or disability 4 Unemployed and looking for work 5 Other (please write in) 6
 
.....
	8

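### The carer measurement schedule contradicts itself, and nothing places carer consent or a first carer GHQ before randomisation

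*Protocol*

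**What the plan says.** Five parts of the protocol bear on when carers are enrolled and measured.

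- **Recruitment.** "Carers will be approached by a researcher with the permission of the patient following the baseline interview". It continues: "If they agree to research consent will be taken and they will be interviewed at the 3 month follow up point". No other carer time point is given there.
- **Randomisation, stratification and assessment.** Once patients consent, "they will be randomised to home based or day hospital rehabilitation following a baseline interview". Carers are not mentioned.
- **Outcome measures.** "All outcomes will be measured at base line and at 3, 6 and 12 months after recruitment", by interviewers blind to allocation. The secondary outcomes include the carer's psychological health on the GHQ. Carer interviews are to fall within a month of the patient's.
- **Carer Interviews.** "It was found in the pilot study that many carers are present" when the patient is interviewed. In that case consent and the carer interview take place then; otherwise a separate visit is arranged. The section does not say which patient visit is meant.
- **Economic Evaluation (other costs to carers) and the Carer Interview Schedule.** The economic text allows the carer interview up to a month after the patient's. The carer form's header offers the time points "Baseline(0)/3 months (1)/6 months(2)/1 year(3".

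The Hypotheses section covers carers as well as patients: neither group is to be disadvantaged by home-based rehabilitation.

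**The concern.** A site following Recruitment would take the first carer GHQ at 3 months. A site following Outcome measures would take it at baseline. A site following Carer Interviews might do either, depending on whether the carer happened to be there. A mixture of carers with and without a baseline is a plausible result.

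Two things are at stake for the carer comparison. The first is a measure of carer distress before treatment, needed to adjust the later GHQ scores and to see whether the two groups of carers started alike. The second is protection against selective enrolment. If the carer is asked after the setting is known, the patient (who gives permission) and the carer (who consents) may respond differently in the two arms. The trial aims to show that carers are not disadvantaged, so a comparison that is imprecise or affected by selection could miss a real disadvantage. A statistical analysis plan cannot supply a baseline that was never taken.

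**Working it through.** The protocol states no carer sample size, GHQ difference or GHQ standard deviation, so there is no planned figure to reproduce. The check is mainly one of timing.

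**1. Is there a baseline carer GHQ?** Recruitment gives 3 months only. Outcome measures gives baseline, 3, 6 and 12 months for every outcome and lists carer GHQ among them. The carer form has a code for baseline. The first cannot be squared with the other two.

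**2. Would a baseline carer interview precede allocation?** The carer approach and the randomisation both follow the patient's baseline interview, and their order is not fixed. The carer interview may then come up to a month later. A carer interview coded as baseline could therefore fall before or after allocation.

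**3. Could the 3-month interview stand in for a baseline?** Research Sites cites a median of 7 weeks in the service, from an unpublished regional day hospital study, and expects 95% of subjects to be discharged within 16 weeks. Three months is about 13 weeks. If treatment starts near randomisation, more than half of patients would have finished by then (13 > 7). A first GHQ at that point is an outcome. A carer interview one month after allocation (about 4 weeks) would also fall well inside the median treatment period.

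**4. What is a baseline worth?** With baseline-to-follow-up correlation r, adjustment removes a share r² of outcome variance. Without it, the number of carers needed for equal precision rises by 1/(1 − r²). The documents give no r, so the range is an assumption.

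| assumed r | variance removed, r² | 1 − r² | carers needed without baseline, 1/(1 − r²) |
|---|---|---|---|
| 0.3 | 0.09 | 0.91 | 1.10 |
| 0.5 | 0.25 | 0.75 | 1.33 |
| 0.7 | 0.49 | 0.51 | 1.96 |

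The size of any selection by arm cannot be calculated from the protocol.

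**The case against.** The best defence is that this is a loose sentence rather than a design fault. The all-outcomes rule cannot be literal, because its list includes survival, change of residence and views of treatment, none of which can be measured at baseline. The time-point line on the carer form also stands on the patient economic form, so it may be carried over from a template. On that view Recruitment is the specific instruction. Part of this stands: either side may be the intended one. But carer GHQ, unlike survival, can be measured at baseline, and the defence leaves the plan either contradictory or without the baseline.

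A reader might go further and infer four things that the protocol does not support.

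- *That carer GHQ has no baseline.* This holds only if Recruitment prevails.
- *That enrolment will depend on allocation.* The text leaves this open and does not say it. Approaching the carer straight after the baseline interview, before allocation, is consistent with the wording. Randomisation is managed independently, and interviewer blinding limits selection by the researcher.
- *That carers form half of a primary hypothesis.* No hypothesis is labelled primary. The primary outcome is the patient's Nottingham EADL score, and carer GHQ is secondary.
- *That the carer groups could not be compared at all.* The carer form records relationship, start of caring, work, marital status and date of birth, most of which can be compared by arm. Patients with and without a participating carer can also be compared on their own baseline data. What would be missing is the carer's distress before treatment.

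The defence is also right on practicality. The economic section allows up to a month to find and contact carers, so making carer consent a condition of randomisation could delay patients.

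**Conclusion.** The contradiction is real and stands in the current text. The carer schedule should be settled before recruitment, because a missed baseline cannot be recovered. As written, the protocol neither guarantees a carer GHQ before allocation nor prevents carers from being enrolled after it. The carer GHQ comparison may therefore lack a true baseline, and enrolment could differ by arm; neither outcome is certain.

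The consequence is limited to the carer comparison: a secondary outcome, but one that the trial hypotheses name. The Nottingham EADL comparison and its sample size are untouched. The factor of about 1.10 to 1.96 in carers rests wholly on the assumed correlation of 0.3 to 0.7. It illustrates the loss and is not needed for the conclusion.

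**What to change.** 1. Reconcile Recruitment, Outcome measures, Carer Interviews, the carer text in the Economic Evaluation and the carer form to one schedule: baseline, 3, 6 and 12 months. Say which visit the carer-present route refers to.
2. Approach the carer at, or straight after, the patient's baseline interview. Take consent and GHQ-30 before allocation is disclosed wherever the carer can be reached. Do not make this a condition of randomising the patient.
3. Record for each carer whether enrolment came before or after allocation. Treat only a GHQ taken before allocation as a baseline.
4. Use baseline GHQ as a covariate in the carer comparison, and report carer participation by arm.

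The cost is one added carer interview, which the pilot put at about 30 minutes, at a visit that many carers already attend. Some carers will still be reached only after allocation and will have no true baseline. Recording the timing at least shows how many there are and in which arm.

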Variability between centres in terms of size of day hospital and patient case mix will provide a robust basis for generalisability. Variability between services will be documented as part of a description of resource use in each centre. Case mix will be monitored during the trial to ensure comparison with other centres. An additional observational study will also provide a context for the research and the research team are currently designing a potential "add-on" study. The impact of services will be measured in terms of both resource use and cost. Costs to patients, informal caregivers and health and personal social services will be estimated. The unit of analysis will be "cost per patient" (see below). Sub-group analysis, will examine the costs and benefits to specific patient groups. The records of patients recruited to the trial will be reviewed independently by one of the applicants (PE), plus an appropriate dual observer, in order to assess differences in professional inputs within and between centres. Where subjects fail to comply with treatment but where compliance with continuing data collection is achieved subjects will be analysed on an intention to treat basis. Clinician compliance, including nursing and therapist involvement will be given high priority by the project manager. A member of the rehabilitation professions among the applicants (PE) will provide support and encouragement for all centres. We will provide regular newsletters to each centre showing target and actual response rates as well as visits from the research team, as mechanisms for encouraging staff compliance.

Sample size

We estimate a sample of 460 patients (230 propoiti and 230 controls) will have 90% power to detect a difference of two points on the Nottingham EADL scale(19) using a significance level of 5%. NRDHS data estimates about a 10% attrition over the course of the study but we have used the more conservative estimate of 15% in estimating sample size, throughput and budgeting for data collection. Therefore allowing for initial non-response of 20% and attrition between times 1 and 2 of 15% we need to recruit 680 patients, probably from 6-8 participating clinical centres.

Analysis

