Analysis of the trial data will be on an 'intention to treat' basis. Univariate and multivariate techniques including survival analysis, non-parametric analysis of variance and log-linear modelling will be used to evaluate the relationships between inputs and outcomes. Interim analysis of throughput, case mix and difference in primary outcome will be done by an independent data monitoring committee 9 and 21 months after recruitment has begun (at the end of the first and second year of the study). We will monitor throughput but all other analysis will wait until the end of data collection.

Economic Evaluation

Perspective of the study

An economic evaluation will be conducted alongside the clinical trial to compare home-based rehabilitation (HBR) vs. day hospital rehabilitation (DHR). DHR is considered to be the current practice. The aim of the study is to test the hypothesis that for older people requiring rehabilitation, HBR: (i) is not less effective than DHR, (ii) is not less preferable than DHR to the patients and their carers, (iii) is less costly than DHR.

The economic evaluation will address the study question from the NHS decision making and societal perspectives (20). We recognise that a decision making perspective is particularly suitable to address the study questions posed by the NHS research programme. However, we believe the societal perspective to be also important because the problem under investigation has an impact on other agents beyond the health service, and the decision maker may want to be informed about such implications.

The societal perspective is aimed at including all costs and health effects regardless of who incurs the costs and who obtains the benefits (21). We will try to make the collection of the most important data to address the societal perspective practically feasible, without making the data collection instruments too cumbersome. Therefore, we will consider the costs (and benefits) to the providers of health and social services, the patients and their carers. Although a wide range of cost items and outcomes will be included, the core analysis will focus on the subsets of costs and effects relevant for allocating the health service budget.

Measures of benefits used and study type

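### NEADL is the primary outcome, but no primary time point is fixed and no named analysis is tied to it that would report a mean difference in points

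*Protocol*

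**What the plan says.** - **Outcome and timing** (Protocol, Outcome measures): "The primary outcome will be functional health status as measured using the Nottingham Extended ADL scale". On timing, "All outcomes will be measured at base line and at 3, 6 and 12 months after recruitment". None of the three follow-ups is singled out. The Sample size section mentions attrition between times 1 and 2, which does not identify a primary visit.
- **Target** (Sample size): "We estimate a sample of 460 patients (230 propoiti and 230 controls) will have 90% power to detect a difference of two points". No SD is given, and the 5% level is not said to be one- or two-sided.
- **Methods** (Analysis): "Univariate and multivariate techniques including survival analysis, non-parametric analysis of variance and log-linear modelling will be used", with the stated purpose of relating inputs to outcomes. The paragraph covers the trial data as a whole and assigns no method to any outcome.
- **Randomisation** (Randomisation, stratification and assessment): blocks within each centre, and "Eligible patients will be stratified by source of referral (hospital inpatient or primary health care team) and the Oxford Handicap Scale", cut at 2/3. The Analysis section mentions neither these factors nor baseline NEADL.
- **Other uses of NEADL**: the Hypotheses section says home rehabilitation does not disadvantage patients. The Economic Evaluation (Measures of benefits used and study type) takes the NEADL score as the benefit in the cost-effectiveness analysis.

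**The concern.** A primary outcome is not fully defined until its time point is. Without one, the 460-patient calculation has no definite target, and neither has the interim look at the difference in the primary outcome that the Analysis section gives to the data monitoring committee. The choice could also be made after results are seen.

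The named methods do not fit what the design has to deliver. The trial is sized on a difference in points. A claim that patients are no worse off rests on where a confidence interval lies on the NEADL scale, which a non-significant rank test does not show. A cost-effectiveness ratio needs an incremental mean. Survival analysis and log-linear models do not estimate a difference in a functional score, and rank analysis of variance is usually reported as a p-value.

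Baseline NEADL will be on file for every interviewed patient and is likely to predict later NEADL well. Leaving it out would widen the interval on which the main claim depends.

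**Working it through.** **1. The plan's own figure.** Inputs from Sample size: 230 per arm, 90% power, difference 2, 5% level (two-sided assumed). The figure of 460 cannot be reproduced because no SD is stated, so I solve for the SD:

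SD = 2 / [√(2/230) × (1.960 + 1.282)] = 2 / (0.0933 × 3.242) ≈ 6.62 points (7.33 if one-sided).

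Standard error of the difference = 6.62 × 0.0933 = 0.617. The 95% CI half-width = 1.96 × 0.617 = 1.21 points.

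**2. Effect of adjusting for baseline.** Residual SD = 6.62 × √(1 − r²), where r is the correlation of baseline with follow-up NEADL. The protocol does not give r; 0.4 to 0.7 is an assumed range. Power = Φ(difference / SE − 1.96).

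| r | √(1 − r²) | Residual SD | Power, 2 points | Power, 1.5 points | CI half-width |
|---|---|---|---|---|---|
| 0 (unadjusted) | 1.000 | 6.62 | 90.0% | 68% | 1.21 |
| 0.4 | 0.917 | 6.06 | 94.3% | 76% | 1.11 |
| 0.5 | 0.866 | 5.73 | 96.3% | 80% | 1.05 |
| 0.6 | 0.800 | 5.29 | 98.2% | 86% | 0.97 |
| 0.7 | 0.714 | 4.73 | 99.5% | 93% | 0.86 |

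The variance falls by r², that is by 16% to 49%.

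**3. Cost of ranks alone.** Under normality the rank test has efficiency 3/π = 0.955. Power with 230 per arm goes from 90% to 88.6%. The power loss from ranks is therefore small; the issues are the missing estimate in points and the unmentioned baseline.

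**4. Open time point.** Suppose each of the three follow-ups is tested at two-sided 5% and success is claimed on any of them. By simulation, the chance of at least one false positive is 11.8%, 10.9% and 9.8% at assumed correlations between the test statistics of 0.6, 0.7 and 0.8. With independent tests it would be 1 − 0.95³ = 14.3%.

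**5. Which time points suit.** The Research Sites section expects 95% of patients to be discharged within 16 weeks, about 3.7 months. The 3-month visit (about 13 weeks) comes before that; 6 and 12 months come after it.

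**The case against.** **The list is open.** It begins with univariate and multivariate techniques and only then gives examples. The examples could belong to other outcomes: survival analysis to death, log-linear models to change of residence, rank methods to ordinal scales. Covariates are commonly settled in a statistical analysis plan, which is not shown. This stands. A reader might infer that the trial will ignore baseline NEADL and the strata, or is committed to rank analysis of variance for NEADL; the text supports neither. Adjustment is unmentioned, not excluded.

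**Rank methods can give points.** Inverting a two-sample rank test gives the Hodges-Lehmann shift and its interval in NEADL points. This also stands, so it would be wrong to say that rank methods cannot yield a difference in points. But that shift is not the difference in means unless a pure location shift holds. The protocol's own costing section (Methods of data analysis) prefers arithmetic means and warns that non-parametric tests can mislead. The effect side of the same cost-effectiveness ratio calls for the same treatment.

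**The gain is hypothetical.** Neither SD nor correlation is stated, and 460 might already allow for adjustment. If so, 6.62 is the residual SD and the gain in the table disappears. The point then turns round: an unadjusted analysis would have SD 6.62/√(1 − r²), that is 7.22 at r = 0.4 and 9.27 at r = 0.7. Power would be Φ(3.242 × 0.917 − 1.96) = 84% and Φ(3.242 × 0.714 − 1.96) = 64%.

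**No any-of-three rule is stated.** Correct. The 10–12% is what the open wording would permit, not what the protocol plans. It also concerns a false claim of difference, which is not the governing error for a claim that patients are no worse off.

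**Conclusion.** The point holds in limited form. Two things are established by the text: no primary time point is fixed for NEADL, and no named method is tied to NEADL that would, as usually reported, give the mean difference and confidence interval needed by the sample size target, the main hypothesis and the cost-effectiveness analysis. The first belongs to the definition of the primary outcome and is not mere analysis-plan detail.

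The silence on baseline NEADL and the randomisation factors is not an error in itself. It is an opportunity to gain precision at no real cost: power for 2 points of about 94–99.5% instead of 90%, and a half-width of 1.11–0.86 instead of 1.21 points. Those figures rest on a back-solved, unadjusted, two-sided SD of 6.62 and an assumed correlation of 0.4 to 0.7. The 10–12% false-positive rate depends further on a decision rule that the protocol does not state.

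A reader might also infer that 6 months should be primary. The document gives no ground for preferring 6 over 12 months, only a reason to look beyond 3. This should be changed, but it does not undermine the design.

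**What to change.** 1. Name one primary time point for NEADL before any comparison of the arms is seen. Either 6 or 12 months falls after the 16 weeks by which 95% are expected to be discharged. Treat the other visits as secondary.
2. Make the primary analysis a linear model at that visit, or a repeated-measures mixed model over 3, 6 and 12 months with the contrast at that visit. Adjust for baseline NEADL, centre, referral source and Oxford Handicap stratum.
3. Report the HBR minus DHR mean difference in NEADL points with its 95% CI, using a bootstrap interval if the scores are skewed. Use the same estimate as the benefit in the cost-effectiveness analysis.
4. Keep rank methods for NEADL as sensitivity analyses, and say which outcomes the survival and log-linear methods are for.

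The cost is wording in the protocol and the statistical analysis plan. Every variable is already collected, and neither the sample size nor the visit schedule changes.
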